Figure 2: Kaplan-Meier estimates of overall survival and progression-free survival by the presence of pseudoprogression

This difference was more pronounced in patients with MGMT methylation) [63]. It is now well recognized that inaccurate attribution of progression or pseudoprogression at enrollment or at the time of response assessment can significantly bias clinical trial outcomes based on progression free survival. In addition, it leads to premature therapy switching, potentially negating the benefits of a particular therapy. These radiographic changes are expected to increase after immune-modulatory therapy like PD-1 inhibitors such as pembrolizumab. A subject on a potentially beneficial immune-modulatory therapy could be taken off a clinical trial because the subject may falsely fulfill RANO or RECIST criteria for progression even though in reality, the radiographic progression could be due to pseudoprogression or response to immunotherapy. This is especially true in trials with immunotherapies where response may be slow or delayed. Figures 1 and 3 show pseudoprogression in glioblastoma. The patient described in figure 3 was on immune-modulatory therapy (EGFRv3 based vaccine study) and was taken off study due to erroneous diagnosis of true progression when the patient in fact had pseudoprogression and subsequently showed clinical and radiographic improvement.

Early ferumoxytol scans: A biomarker for tumor vascularity

[figure not shown]

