8.0 RESPONSE ASSESSMENT, IMAGE PROCESSING AND BIOMARKERS

8.1 Definitions for Response assessment:

The study will use the following criteria for the assessment of brain lesions.

Complete response (CR): Complete disappearance of all enhancing abnormalities on clinical enhanced MRI scan (in the absence of gadolinium, ferumoxytol enhancement will be used). Some subjects will have a small but persistent enhancing abnormality on MRI related to biopsy or focal hemorrhage. It is often difficult to ascertain whether this represents a residual nidus of tumor or scar tissue. Adjunctive radiologic studies such as SPECT or PET as clinically indicated may be helpful, but often the nature of these abnormalities may only be determined by following the subject with serial scans. If this type of abnormality does not change or slowly involutes over time off therapy and corticosteroids, it is reasonable to categorize it as a CR.

Partial Response (PR): At least 50% decrease in the contrast enhancing lesion seen on MRI as compared to baseline imaging. In the event of multiple lesions, the determination of partial response will be based on the sum of the bi-dimensional measurements (greatest diameter x greatest perpendicular) across lesions AND no new sites of disease

Stable disease (SD): less than a PR but is not progressive disease.

Progressive disease (PD):

- **Suspected Radiographic Progression:** progression will be defined by a 20% increase in volume of enhancement compared to the best response on clinical standard of care MRI. At any time point if progression is suspected on the clinical scan, additional steady state ferumoxytol MRI will be performed within 7 days of the clinical scan. Progression will then be confirmed with a follow up scan in 4 weeks \pm 5 days with a clinical standard of care MRI scan and additional ferumoxytol scan.
- **Persistent Radiographic Progression:** sustained and evident progression greater than increase in volume of enhancement compared to best response on a follow up scan at least 4 weeks after the scan where progression was suspected as per RANO BM form arm 1 or RANO criteria for subjects in arm 2. In cases with persistent radiographic progression the date of initial scan when progression was suspected will be considered to be the date of progression.
- Appearance of any new lesion or site of disease in the brain during or at the end of therapy.

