- **Confirmation of true progression:** For the purpose of this study, Histopathologic evidence of viable tumor cells in patients with persistent radiographic progression will be define to have confirmed true progression. True progression is confirmed by histopathology, Pembrolizumab will be stopped and patient swill be taken off-study.. Patients who refuse biopsy or biopsy is not deemed clinically necessary will be taken off study at persistent radiographic progression. However, they will be continued to be monitored with clinical MRI scan and until death.
- **Pseudoprogression (PsP):** for the purpose of this pilot study, PsP may be confirmed by imaging or by pathology.
 - PsP Imaging: stable or decrease in volume of enhancement at 4 weeks (\pm 5 days) after suspected radiographic progression.
 - PsP pathology: No viable tumor tissue is seen by histopathology evaluation on tissue obtained after confirmed radiographic progression by imaging.
- **Clinical progression:** Subjects may be removed from study if they experience symptomatic deterioration without radiographic evidence of disease progression.

Not evaluable (NE): Only relevant if any of the target lesions had additional interventions for clinical managements, patient is unable to get follow up scans or images are of poor quality.

Duration of Best Response: The duration of best response is measured from the time measurement criteria are met for SD, CR or PR (whichever is first recorded) until the first date that recurrent or PD is objectively documented (taking as reference for PD the smallest measurements recorded since the treatment started).

Progression free survival and overall survival will be calculated from the date of diagnosis to the date of confirmed progression or death, respectively. The date of diagnosis was used because the time between the date of diagnosis and the start of treatment or date of enrollment may vary due to subject variables or logistical issues based on radiation planning.

Systemic Lesions (only for Arm 1):

Measurements based on RECIST version 1.1 will be used to make a diagnosis of suspected systemic progression; it will be confirmed using irRC at follow-up.

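### Section 8.1 has no rule that keeps pseudoprogression from ending duration of best response, and does not say whether confirmed progression for PFS means by scan or by tissue

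*Combined protocol and SAP*

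**What the plan says.** Section 3.2 makes PFS, clinical response and duration of best response secondary objectives, and says the data will be used to power a larger study. The endpoint rules are in Section 8.1.

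- **Suspected radiographic progression** is the first item under the PD heading: "progression will be defined by a 20% increase in volume of enhancement compared to the best response on clinical standard of care MRI". The same item calls for a follow-up scan 4 weeks later to confirm it.
- **Persistent radiographic progression** comes next and carries the dating rule: "In cases with persistent radiographic progression the date of initial scan when progression was suspected will be considered to be the date of progression".
- **Pseudoprogression** sits in the same list. It may be established by imaging (enhancement stable or smaller at 4 weeks) or by pathology, the latter defined as: "No viable tumor tissue is seen by histopathology evaluation on tissue obtained after confirmed radiographic progression by imaging".
- **Duration of best response** runs from the first record of SD, PR or CR "until the first date that recurrent or PD is objectively documented", "taking as reference for PD the smallest measurements recorded since the treatment started".
- **PFS and OS** run from diagnosis "to the date of confirmed progression or death, respectively".

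Section 10 adds Kaplan-Meier estimation with censoring, but does not say what counts as a PFS event or as the end of a response.

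**The concern.** The trial exists to tell pseudoprogression from true progression, and Section 4.0 itself warns of bias in PFS: "inaccurate attribution of progression or pseudoprogression at enrollment or at the time of response assessment can significantly bias clinical trial outcomes based on progression free". Yet no endpoint rule removes an episode once it has been shown to be pseudoprogression. A subject whose tissue shows no viable tumour continues pembrolizumab (Sections 2.0, 6.0, 7.4 and 7.6), so the protocol manages that subject as not progressed. Nothing in 8.1 or Section 10 cancels the progression date already assigned.

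If refuted progressions count, both endpoints are biased short, and most so in subjects with an inflammatory response. If progression counts only when tissue proves it, PFS is biased long, because progressions in unoperated subjects drop out. Leaving the choice until analysis also allows it to be made with the results in view.

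**Working it through.** **Inputs, all from the Arm 2 sample size text in Section 10.** N = 43; 32 subjects with surgery; 26 of those 32 with true progression on pathology; pseudoprogression in 40%.

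**The plan's own figures.** 0.40 × 43 = 17.2, which the plan gives as 17. Exact (Clopper-Pearson) intervals are 65.1% to 95.6% for 22/26 = 84.6%, and 63.6% to 98.5% for 15/17 = 88.2%. Both agree with Tables 12 and 13. The plan states no figure for PFS or duration of response, so the rest is a check of definitions followed by a count of subjects.

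**Step 1: duration of best response.** The rule takes the first date on which PD is documented. The PFS sentence that follows requires confirmed progression; the duration sentence does not. Its reference, the smallest measurement, is close to the best-response reference used for suspected progression. On the literal text, the suspicion scan therefore ends the response, whatever the 4-week scan or tissue later shows.

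**Step 2: PFS.** The documents use *confirmed* in two ways:

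- By scan: Sections 2.0 and 6.0 (the 4-week scan confirms progression), Section 5.4 (imaging or biopsy suffices), and the pathology definition of pseudoprogression in 8.1, which presupposes progression already confirmed by imaging.
- By histology: the 8.1 item on confirmation of true progression, which requires viable tumour cells.

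The date-back rule applies to every persistent radiographic progression and makes no exception for tissue that shows pseudoprogression. Imaging pseudoprogression fails the 4-week scan, so it is not a PFS event on either reading.

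**Step 3: subjects affected.**

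- Operated without true progression: 32 − 26 = 6. The plan does not call these 6 pseudoprogression; that is assumed here. Nor does it say whether they are among the 17, hence the range below.
- Duration of response, literal reading: up to 17/43 = 39.5% if the 17 include the 6, or up to (17 + 6)/43 = 23/43 = 53.5% if they do not. These are upper limits, since a response must have been recorded before the suspicion scan.
- PFS, confirmed by scan: up to 6/43 = 14.0% false events, or 6/32 = 18.8% of operated subjects. Imaging pseudoprogression adds none.
- PFS, confirmed by histology only: no pseudoprogression events, but at most 26/43 = 60.5% of subjects can have a progression event. The 43 − 32 = 11 without surgery never can.

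**Step 4: what cannot be computed.** The documents give no event times for progression or pseudoprogression, so the change in median PFS, in PFS at a fixed time, or in response duration cannot be derived.

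**The case against.** The PD list is loosely built. It also contains pseudoprogression and clinical progression, so a place in the list does not make each item a PD event. The suspected-progression item is provisional in its own terms, and the dating rule is written only for persistent progression, which would be needless if the suspicion scan were already a dated PD. For PFS, 8.1 defines confirmed true progression by histology, and subjects with pseudoprogression on tissue continue treatment. The endpoints are descriptive, in a pilot that tests no formal hypothesis.

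Much of this stands. A reader might infer that pseudoprogression definitely ends both endpoints, or that all 17 expected pseudoprogressions become PFS events. The documents do not support either. Imaging pseudoprogression never reaches confirmed progression, and the tissue cases depend on one of two available readings. A reader might also want to state months of PFS lost; without event times, any such figure would come from assumed inputs, not from the plan.

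What the objection does not supply is a rule. The duration sentence omits confirmation, no text reverses a scan-confirmed date, and the histology reading that would spare PFS from false events leaves the unoperated subjects with no way to progress.

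**Conclusion.** The point holds as a defect in the endpoint definitions. Read literally, pseudoprogression can end duration of best response in up to 17 of 43 subjects, or up to 23 if the 6 operated subjects without true progression are additional. For PFS the text is ambiguous, and both readings fail: up to 6 of 43 false events (14%) if confirmed means by scan, or 11 of 43 subjects unable to have a progression event if it means by histology only. The counts rest on the plan's own planning numbers and on treating those 6 operated subjects as pseudoprogression.

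The primary sensitivity and specificity analysis has its own reference standard in Section 10 and is unaffected. This should be fixed, but it is not critical: the endpoints are secondary and descriptive, and they matter mainly because they are meant to inform a larger study.

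**What to change.** For endpoint analysis only, with no change to treatment rules, put one event definition in 8.1 and Section 10 for PFS, best response and duration of response:

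- PD is (a) histologically confirmed true progression, (b) persistent radiographic progression with no tissue result, or (c) a new lesion, as 8.1 already lists. Events under (a) and (b) are dated to the suspicion scan; the date for (c) should be stated too.
- Suspected progression is a provisional state. An episode classed as pseudoprogression, by imaging or pathology, is not an event, and the subject stays at risk until a later qualifying progression.
- For inconclusive tissue, follow the protocol's own handling in Sections 2.0 and 6.0, where the subject continues until further progression is suspected. Add a sensitivity analysis that counts it as an event.

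The cost is a few lines of text, written before analysis, and no new data. The one small drawback is that the status of an open episode is settled only after the 4-week scan or the pathology result.

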3.0 OBJECTIVES

3.1 Primary Objective

Determine the sensitivity and specificity of relative cerebral blood volume (rCBV) measured by steady state MRI with ferumoxytol in identifying true vs pseudoprogression in patients with newly diagnosed GBM receiving pembrolizumab with standard of care chemo-radiation.

3.2 Secondary Objectives:

1. Determine the safety and toxicity of pembrolizumab when used in combination with standard of care chemo radiation.
2. Determine the progression free survival (PFS), overall survival (OS), clinical response and duration of best response.

Rationale: Given the relatively small sample size, we aim to collect preliminary data on safety and toxicity as well as progression free survival, overall survival, best response and duration of best response survival. Data from this pilot study will be used to power a larger study.

3.3 Exploratory Objectives:

1. Compare the immune response as determined by the volume, pattern and intensity of delayed (24hr) ferumoxytol uptake between subjects who develop true vs pseudoprogression. This is optional and will be performed only in patients who have provided additional consent.
2. Investigate the serum immunological parameters (serum biomarker) and correlate clinical as well as radiological response with systemic immune response to pembrolizumab as measured by immunological panel.

3. Compare the changes in PDL-1 expression in the biopsy tissue before and after therapy at the time of progression and correlate PD-L1 expression with response rates and survival.
4. In subjects in metastatic arm with any measurable systemic lesions, investigate the feasibility of measuring vascular volume fraction (VVF), vessel size index (VSI) and vessel density index (VDI) as surrogate for response (true vs pseudoprogression, as determined by RECIST 1.1 and irRC [1, 2].

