For specificity, it will be calculated based on patients with pseudo-progression determined by either surgical results or follow-up scan. We assume that 40% of the subjects (n = 17) will develop pseudo-progression, then if we observe 15 subjects (lesions) for whom the pseudo-progression status is correctly identified by ferumoxytol MRI, the specificity will be 88% with a 95% CI between 64% and 99% (Table 13).

Number of lesions with pseudo-progression	Number of Lesions with pseudo-progression detected by Ferumoxytol MRI	Specificity	Exact 95% CI of Specificity
17	17	100%	80% to 100%
17	15	88%	64% to 99%
17	13	76%	50% to 93%
17	11	65%	38% to 86%

Table 13: Estimated specificity and 95% CI based on 17 patients.

Statistical Analysis

For arm 2, sensitivity, specificity, rate of adverse events (safety and tolerability) and the distribution of best responses will be analyzed using proportions and exact 95% confidence intervals. In the primary analysis of sensitivity and specificity, the cutoff for rCBV will be specified as 1.75 (<1.75 is pseudoprogression and ≥ 1.75 is progression). Analysis of sensitivity will be based on patients with surgical results, and specificity analysis will be based on patients with pseudo-progression determined based on surgical results or follow-up clinical scan, as detailed in the power and sample size calculation section. In secondary analysis, we will try other cutoff points for rCBV, and include all patients that will be confirmed with true progression through surgery or follow up imaging. Progression free survival and overall survival will be assessed using the Kaplan-Meier product limit estimates for all patients, taking censoring into account. For exploratory objectives, continuous variables will be summarized

using mean and standard deviation, or median and range based on the distribution of data. The categorical variables will be summarized using frequencies and proportions, with exact 95% CI as appropriate.

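### PFS as defined in Section 8.1 does not count a death without confirmed progression as an event, so the reported PFS will run long

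*Combined protocol and SAP*

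**What the plan says.** **PFS and OS.** Section 8.1 states: "Progression free survival and overall survival will be calculated from the date of diagnosis to the date of confirmed progression or death, respectively". It gives a reason for the starting point: "The date of diagnosis was used because the time between the date of diagnosis and the start of treatment or date of enrollment may vary". Section 10 adds only the method: "Progression free survival and overall survival will be assessed using the Kaplan-Meier product limit estimates for all patients, taking censoring into account". It gives no rule for what is censored and when.

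**Progression.** For persistent radiographic progression, Section 8.1 says "the date of initial scan when progression was suspected will be considered to be the date of progression". A separate item in 8.1 reserves confirmed true progression for histological evidence of viable tumour. Patients without a biopsy leave the study at persistent radiographic progression.

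**Clinical progression.** "Subjects may be removed from study if they experience symptomatic deterioration without radiographic evidence of disease progression". Whether this is a PFS event is not stated.

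**Duration of best response.** The clock is "measured from the time measurement criteria are met for SD, CR or PR (whichever is first recorded") and it runs "until the first date that recurrent or PD is objectively documented". Death is not named as an end.

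**Use.** PFS, OS and duration of best response are secondary objectives. Section 3.2 says of the results: "Data from this pilot study will be used to power a larger study".

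**The concern.** Read as written, the definition estimates time to confirmed progression and calls it PFS. A subject who dies without confirmed progression cannot be followed further. A Kaplan-Meier analysis that does not count the death can only censor it, at the very moment the subject fails. That censoring is informative and moves the curve in one direction, upward. Clinical progression may be treated the same way, because nothing in the plan settles it.

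The word confirmed adds a second opening. An analyst who takes it from the histology item in 8.1 would never count a progressor who had no surgery. Two analysts could produce different PFS curves from the same data.

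The trial has one arm, so no comparator shares the bias and cancels it. An inflated median would pass straight into the design assumptions of the next study.

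**Working it through.** The documents give no median, event count or hazard for these endpoints, so there is no stated figure to reproduce. Every size below rests on an input labelled as assumed, or on the plan's own counts.

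**1. Death and clinical progression not counted.** Let the total failure hazard be λ and let s be the share of first failures that are deaths or clinical progression without confirmed progression.
- True median PFS: M = ln 2 / λ.
- If those failures are censored, Kaplan-Meier tracks the hazard (1 − s)λ, and its median is M/(1 − s).

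With M = 7 months (assumed):

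| s (assumed) | factor 1/(1 − s) | median, months | 6-month PFS, 0.5^(6(1 − s)/7) |
|---|---|---|---|
| 0 | 1.00 | 7.0 | 55.2% |
| 5% | 1.05 | 7.4 | 56.9% |
| 10% | 1.11 | 7.8 | 58.6% |
| 20% | 1.25 | 8.8 | 62.2% |
| 30% | 1.43 | 10.0 | 66.0% |

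The factor does not depend on M.

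**2. Histology-only reading of confirmed.** Section 10 enrols 43 subjects, assumes that all eventually progress, and expects 32 to have surgery. That leaves 43 − 32 = 11, or 11/43 = 26%, who could not have histological confirmation. If all 11 progressed and were censored at that point, the factor under constant hazards would be 43/32 = 1.34. This is an illustration, not an estimate, because Section 10 attributes the shortfall to dropout as well as inoperable disease.

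**3. Time origin.** Section 5.2 requires histological diagnosis before entry, ECOG 0 or 1, and a life expectancy of at least 6 months. A patient who dies or declines between diagnosis and enrolment never enters. Under constant hazards, a lag of w weeks adds w × 7/30.4375 months to the median compared with a clock that starts at enrolment. The lag is not given. Assumed values of 2, 4, 6 and 8 weeks add 0.46, 0.92, 1.38 and 1.84 months. That is +7% to +26% of a 7-month PFS, or +3% to +12% of a 15-month OS (both medians assumed).

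**4. Points 1 and 3 together**, from M = 7 months:
- s = 5%, 2 weeks: 7/0.95 + 0.46 = 7.8 months.
- s = 20%, 4 weeks: 7/0.80 + 0.92 = 9.7 months.
- s = 30%, 8 weeks: 7/0.70 + 1.84 = 11.8 months.

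Simulating the same set-ups gives 7.84, 9.69 and 11.82.

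**5. Duration of best response.** Section 6.0 schedules clinical MRI every 9 weeks after the first post-radiation scan. A responder first recorded as stable gains a nominal 9 × 7/30.4375 = 2.07 months per scheduled scan between SD and CR or PR. In a simulation where 70% of responders have SD one or two scans earlier (assumed), the responders' median moves from about 9.0 to 11.3 months.

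The pooled figure has no fixed direction. With 20% responders (assumed):
- CR/PR median 9 months, SD-only median 5: the pooled SD, PR and CR median is 6.0, below the CR/PR-only figure.
- CR/PR median 6 months, SD-only median 9: the pooled median is 8.8, above it.

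**The case against.** The best case for the plan is that the PFS sentence is loosely worded, that any oncology statistician would count death, and that Section 10 assumes every subject eventually progresses. If that assumption held exactly, s would be 0 and the factor 1. The endpoints are secondary, there is no formal hypothesis, and the analyses are declared descriptive. Even with events in all 43 subjects, an exponential median has a 95% interval of about exp(±1.96/√43), or 0.74 to 1.35 times the estimate. That is as wide as most of the bias shown.

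Part of this stands. The primary sensitivity and specificity analysis is untouched, and the size of s is unknown. But nothing elsewhere in the plan makes death a PFS event. If s is near 0, the correction costs nothing. Sampling error is reported with an interval, whereas this bias is not visible in one.

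The histology-only reading is open but is not the better one. Section 5.4 describes confirmed progression as confirmed by imaging or biopsy.

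The diagnosis origin is a disclosed choice with a stated reason. That answers why it was chosen but does not remove the unobservable time: a variable lag means variable credited time.

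A reader might infer more than the documents support:
- **That two progression dates differ by four weeks or more.** Section 8.1 back-dates persistent progression to the first suspected scan, so the confirmation wait does not lengthen PFS.
- **That the censoring problem inflates OS.** OS ends at death; only its origin is in question.
- **That subjects removed for clinical deterioration are certainly censored at removal.** Section 7.4 follows all subjects with examination and MRI until death or loss to follow-up, while 7.10 describes survival contact only. The text is unclear.
- **That subjects replaced under 5.4.3 drop out of PFS and OS.** Section 10 specifies all patients.
- **That the 14 days in inclusion criterion 6 are a minimum lag from diagnosis.** They run from surgery or biopsy to first pembrolizumab, and the documents do not equate that surgery with the date of diagnosis.

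**Conclusion.** The PFS definition is wrong as written and biases PFS upward whenever a subject dies without confirmed progression. Clinical progression is left undefined and adds to the bias if it is not counted. The factor is 1/(1 − s): +5% to +43% for s from 5% to 30%, with s assumed and hazards constant.

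The diagnosis origin without delayed entry adds the unreported diagnosis-to-enrolment lag to PFS and OS, about 0.5 to 1.8 months for an assumed 2 to 8 weeks.

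Duration of best response is inflated for responders first recorded as stable. It would be wrong to conclude that all three endpoints are overstated: for a subject whose best response is SD, starting at first SD inflates nothing, and the direction for the pooled median is undetermined.

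This should be corrected before analysis because the results feed a larger study. It does not threaten the trial's primary objective.

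**What to change.** **PFS event (8.1, repeated in Section 10).** Define it as the first of:
- persistent radiographic progression, dated at the scan where it was first suspected, as 8.1 already provides, and not requiring histology;
- clinical progression;
- death from any cause.

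Episodes shown to be pseudoprogression are not events. Censor event-free subjects at their last assessment. Because 8.1 also lists a new brain lesion as progressive disease, say how it is dated.

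**Origin.** Keep diagnosis as the origin with delayed entry at enrolment, or also report PFS and OS from first dose. Report the distribution of the lag either way. Delayed entry removes only lag beyond the earliest entry time, and early risk sets will be small with 43 subjects, so the first-dose curve is the easier one to read.

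**Duration of response.** Report it from first CR or PR in responders, give SD duration separately, and state how death is handled.

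**Cost.** Wording in 8.1 and Section 10, with no new data. The reported PFS will be shorter.
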